
The exercise intervention is no more intense than what most participants would encounter walking during their normal day-to-day activities. The participants will be closely monitored and the intervention stopped for any subjective or objective evidence of discomfort. Participants involved in this study will have been screened for any medical conditions that would increase their risk of any negative effects from the exercise intervention.

Five to fifteen minutes after the exercise intervention has been completed blood will again be collected in exactly the same manner as the resting sample. Participants will then receive a 2 week supply of either NutraStem or placebo and will be advised to take one tablet every morning and evening before meals for the next 2 weeks. Participants will be advised to bring their empty pill containers to their next session so we can confirm they are taking the supplement as required. Those that complete the 1st session will receive \$40.00 compensation. If the participant is unable to complete any portion of the visit activities at any visit they will be withdrawn from the study due to their

inability to complete the study. All visit activities will be recorded in detail on the visit session record.

The second visit will occur 2 weeks later and include a blood pressure check, an at rest blood draw, the exercise intervention, and then a repeat blood draw five to fifteen minutes after completion of the intervention. Participants will then receive a 2 week supply of either NutraStem or placebo and will be advised to take one tablet every morning and evening before meals for the next 2 weeks. Participants will be advised to bring their empty pill containers to their next session so we can confirm they are taking the supplement as required. If the blood pressure is outside of the specified range they will be dropped from the study and no blood collection or study intervention will take place. They will receive \$20.00 compensation for the visit. Those that complete the 2nd session will receive \$60.00 compensation.

The third visit will be the same as the second visit. If the session cannot be completed due to failed blood pressure screen participants will receive \$20.00. All participants that complete the 3rd session will receive \$80.00.

SESSION	ACTIVITIES	VISIT LENGTH	COMPENSATION

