This certificate is the property of NSF International and must be returned upon request. Products are evaluated and company is audited for compliance at regular intervals. To verify registration visit www.nsf.org

Scientific description of the ingredients of the product per a 2 capsule dose

Proprietary Blend – 900mg:

Vitamin D3 (as cholecalciferol) – 2000 IU
 BioVin® Grape Extract – 40 mg
 Green Tea Extract (*Camellia sinensis*)
 Wild Blueberries* (whole fruit)
 Carnosine
 VitaBlue® Wild Blueberry Extract*
 **Vaccinium angustifolium*

Other Ingredients:

Magnesium stearate, Cellulose (vegetarian capsules)
 Contains no yeast, wheat, corn, milk, egg, soy, glutens, artificial colors or flavors, added sugar, starch or preservatives.

Reported Adverse Events and Potential Risks

Although the ingredient combination within NutraStem®'s patented formulation has not undergone human clinical trials at this point, the individual ingredients are well-established as safe with very few adverse effects, side effects, or potential risks. Each ingredient is listed below accompanied by its reported adverse events/side effects. In some instances the dose of that ingredient supersedes the amount within the NutraStem® formulation. This list includes Vitamin D3, BioVin® and the ingredients comprising the proprietary formulation, Green Tea Extract, Wild Blueberry Extract, VitaBlue®, and L-Carnosine.

Vitamin D3 (as cholecalciferol; 2000 IU) Adverse Events:

According to the National Institutes of Health (NIH) factsheet on Vitamin D3, the tolerable levels are 2,000 IU or international units (11). Thus, this study is within the approved levels of Vitamin D3. Vitamin D3 toxicity can cause nonspecific symptoms such as nausea, vomiting, poor appetite, constipation, weakness, and weight loss (12). It can also raise blood levels of calcium, resulting in confusion and heart rhythm abnormalities (13).

The use of supplements of both calcium (1,000 mg/day) and vitamin D (400 IU/day) by postmenopausal women was found to have a 17% increase in the risk of kidney stones over a 7 year period (14). Deposition of calcium and phosphate in the kidneys and other soft tissues can also be caused by excessive vitamin D levels (15). Although Vitamin D3 is absorbed via sunlight, excessive sun exposure does not cause vitamin D toxicity (16).

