Chez et al. (37) reports that manic or hyperactive autistic patients may show signs of over stimulation, including increased irritability, hyperactivity, or insomnia, when given higher doses of L-Carnosine. Symptoms usually respond by decreasing either the dose of L-Carnosine or other medications concurrently. No permanent negative physical changes have been noted in over 1,000 children treated with L-Carnosine since June of 2001. Furthermore, Chez reports no signs of adverse liver, blood, kidney, or central nervous system side effects.

Potential Risks:

Carnosine is considered an extremely non-toxic and safe substance. As with other antioxidants, carnosine acts synergistically when taken with other antioxidants, however, even with this understanding we do not predict any attributable adverse effects to carnosine. Side effects and/or adverse events are not anticipated or expected, but the study coordinator will closely monitor for this possibility.

Rationale for Dose Selection and Administration

We have selected the dose of two capsules per day in this clinical trial. This is based upon our previous experience with the animal models using this compound (Acosta et al.,unpublished observations), as well as previous research that has used concentrated blueberry extract among human (38). Based on these studies, our rationale for dose selection was to maximize bioavailability and the opportunity to observe efficacy, while minimizing toxicity. Participants will be instructed to take the agent in divided doses of one capsule twice a day before meals for 4 weeks.

Availability

NT-020 capsules are an investigational agent supplied by Natura Therapeutics, Inc.

Agent Distribution

Agents will only be released after documentation of IRB approval of the protocol and consent is provided to the sponsor, University of South Florida and the collection of all essential documents is complete.

Agent Accountability

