The PI, or a responsible party designated by the investigator, will maintain a careful record of receipt, disposition, and return of all study drugs on the Investigational Agent Accountability Record. All study drug supplies will be kept by the UNT pharmacist, [name] and study coordinator, [name], in a locked, limited access area. The study drug will not be used outside the context of the protocol. Under no circumstances will the investigator or other site personnel supply study drug to other investigators, patients, or clinics, or allow supplies to be used other than directed by this protocol. Study agent will not be transferred from one participant to another.

The investigator will maintain records documenting the receipt, use, loss or other disposition of the investigational product, including batch or code numbers, and account for it's disposition on a subject-by-subject basis, including specific dates and quantities.

The source document, documenting the subject's participation in this randomized clinical trial, must be documented in the medical and research records. Destruction will be documented in accordance with institutional SOPs.

Packaging and Labels

NT-020 capsules are packaged with 60 capsules per bottle in 150 cc white HDPE bottles. Bottle labels include agent name, protocol number, dosing and storage instructions, required warnings for restricted, investigational use, and spaces for recording the subject registration and randomization number.

Storage

NT-020 capsules will be stored in a secure location at room temperature [between 59°F and 86°F (15–30°C)].

Side Effects:

All participants will be advised at every visit that if they experience any side effects they feel are related to the supplement they should stop the supplement immediately and consult their health care provider. We will ask that they notify the research coordinator after they have consulted their provider.

Placebo

The placebo is identical in appearance to the NutraStem® supplement and contains the following ingredients in a Vegi Capsule:

MCC200
DICALCIUM PHOSPHATE
BROWN LAKE BLEND (SENSIENT # 09127)
RED DYE DB-088 (COLORCON)
MAGNESIUM STEARATE
BLUE #1 ALUM LAKE (POWDER)

Exercise stimulus

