Exercise will consist of 2 minutes of stretching/warm up consisting of marching in place for 60 seconds followed by 10 toe touches. The exercise intervention will consist of a 15 minute period of walking on a treadmill. The treadmill will not be inclined during the intervention. The participants target heart rate will be determined by deducting their age from 220. They will start walking on the treadmill at a speed of 1.7 mph and the speed will be titrated as indicated to keep their heart rate at 50 to 90% of target. Heart rate will be monitored via the pulse oximetry feature of the Welch Allyn vital signs monitor. Blood pressure will be measured every 3 minutes during the exercise intervention and until they have returned to baseline (within 10 points) following cessation of the exercise protocol. The test will be stopped for any participant complaint of chest pain, excess fatigue, difficulty breathing, a blood pressure reading of more than 180/94, or a participant request. If symptoms increase or do not completely resolve with 15 minutes of rest the study coordinator will call 911 (through campus police) to activate the EMS response. If symptoms resolve completely within 15 minutes participants will be withdrawn from the study and advised to follow up with their health care provider. Any participant unable to complete the exercise intervention for any reason will be withdrawn from the study.

The exercise intervention is no more intense than what most participants would encounter walking during their normal day to day activities. The participants will be closely monitored and the intervention stopped for any subjective or objective evidence of discomfort. Participants involved in this study will have been screened for any medical conditions that would increase their risk of any negative effects from the exercise intervention.

Data Analysis/Data Monitoring

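### The only specified route for reporting supplement side effects between visits is filtered by participant attribution and a provider consultation, so adverse events will probably be under-counted

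*Combined protocol and SAP*

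**What the plan says.** The reporting procedure is in section E under Side Effects. At every visit participants are advised what to do "if they experience any side effects they feel are related to the supplement". The instruction that follows ends: "We will ask that they notify the research coordinator after they have consulted their provider".

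Under Reported Adverse Events and Potential Risks, the protocol states that the ingredient combination "has not undergone human clinical trials at this point". The Potential Risks paragraphs for vitamin D3, BioVin, green tea extract, blueberry and L-carnosine each close with the same assurance: "Side effects and/or adverse events are not anticipated or expected, but the study coordinator will closely monitor for this possibility". None of the five gives a question, form, timing or grading.

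The second visit is to "include a blood pressure check, an at rest blood draw, the exercise intervention, and then a repeat blood draw", after which product is supplied for two more weeks. The third visit is described as the same. Neither this description, the visit table nor the screening script includes a question about adverse events. The reminder call described under Recruitment covers appointment details and fasting.

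Data Analysis/Data Monitoring plans means with standard errors and repeated-measures ANOVA for quantifiable results. It names no adverse-event summary.

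Safety is observed directly during the treadmill sessions: "The test will be stopped for any participant complaint of chest pain, excess fatigue, difficulty breathing, a blood pressure reading of more than 180/94", or at the participant's request.

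**The concern.** The written path has two filters in sequence. The participant must first judge that the supplement caused the symptom, and the study is then to be told after a provider has been consulted. An event put down to something else, or too mild to take to a provider, has no specified route into the data.

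Self-attribution is a weak filter here. The complaints listed in the protocol's own risk text, such as nausea, headache, dizziness and indigestion, are common and easily blamed on other causes. For a combination without a prior human trial, the unexpected events matter most, and those are the ones a participant is least likely to attribute. The Blood Analysis section names stem cells, a lipid panel and inflammatory and oxidative markers, but no safety chemistry, so symptom reports carry most of the safety information. A low count could then be read as reassurance when it partly reflects how events were collected. Missed events cannot be reliably recovered afterwards.

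**Working it through.** The plan states no expected adverse-event rate, capture rate, alpha or power, so there is no figure to reproduce. What follows is illustration.

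**Inputs from the documents:** up to 30 participants per arm, double blind (section E); 4 weeks of dosing with visits at 0, 2 and 4 weeks.

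**Assumptions:** the full 30 are enrolled on active; a fraction *f* of participants with an event is captured; event rates are as given below; tests are two-sided at 5%.

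**1. What zero reports would exclude.** The exact one-sided 95% upper bound on the reported rate with 0 of 30 is 1 − 0.05^(1/30) = 0.095. The reported rate is the true rate times *f*, so the bound on the true rate is 0.095 / *f*.

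**2. Chance of seeing at least one report** when the true rate is 10%: 1 − (1 − 0.10 *f*)^30.

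| Capture *f* (assumed) | Upper bound on true rate | Chance of at least one report |
|---|---|---|
| 1 | 9.5% | 96% |
| 0.5 | 0.095 / 0.5 = 19% | 79% |
| 0.25 | 0.095 / 0.25 = 38% | 53% |

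**3. Plausible capture.** If capture is attribution (assumed 0.3 to 0.7) times provider visit and notification (assumed 0.2 to 0.8), it runs from 0.3 × 0.2 = 0.06 to 0.7 × 0.8 = 0.56. This treats the provider step as a strict condition. The text only sets an order of events, so the range leans pessimistic.

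**4. Effect on the comparison when capture is equal in both arms.** Assume true rates of 10% on placebo and 30% on active, with 30 per arm.
- Full capture: expected counts 3 and 9, risk ratio 3.0, risk difference 20 points, Fisher exact power 37%.
- Half capture: expected counts 1.5 and 4.5, risk ratio still 3.0, risk difference 10 points, power 9%.

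**5. Effect when capture differs.** Assume a true rate of 30% in both arms. With 30% capture in each arm, the Fisher false-positive rate is 0.8%. With 60% capture on active and 20% on placebo, as might follow partial unblinding, it is 14%.

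**The case against.** A reader might infer that side effects reach the study only by this route. The documents do not support that. The coordinator, a registered nurse, observes symptoms and blood pressure directly at all three exercise sessions, with no attribution or provider step. The close-monitoring statements carry no such condition either, and visit activities are to be recorded in detail. The advice is also repeated face to face at every visit, so the subject is raised, though as advice rather than as a question. What stands is narrower: for events between visits, this is the only reporting path actually specified.

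A reader might also infer that someone who stops for a mild symptom without seeing a provider is never counted. That goes too far. Participants are asked to bring their empty containers to the next session, so leftover product could reveal stopping and prompt a question. Asking for notification after a consultation does not bar a report from someone who had none.

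The strongest reading, that the arms cannot be compared, does not follow. Both arms are under the same rule, and the placebo is described as identical in appearance. Equal under-capture costs precision and shrinks absolute differences, but leaves the expected risk ratio alone. Nothing in the documents shows that capture would differ by arm. Power for adverse events is low at this size even with full capture.

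It is also fair to say that the advice to participants is not itself a counting rule, and that no by-arm safety table is planned which could mislead. The aim is stem cell levels and oxidative protection. The protocol also mentions a commercially available human dose, which softens the emphasis on first human use, although it does not contradict the statement that there has been no trial.

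Finally, the consent form, the visit session record and a short part of the protocol after the section H heading were not available. They may contain further procedures.

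**Conclusion.** The point holds as a probable under-count. The one specified path for supplement side effects between visits is filtered twice, and the promised monitoring has no stated method. No adverse-event question or by-arm summary appears in the visit descriptions or the analysis section. Half capture would double the rate that zero reports can exclude, from 9.5% to 19%, and halve any absolute difference between arms. These sizes rest on assumed capture fractions and event rates and on full enrolment of 30 on active; the direction does not depend on the exact values. The comparison between arms survives with less precision, and its risk ratio is biased only if capture differs by arm. Efficacy conclusions are not affected. This is a worthwhile, inexpensive improvement, subject to what the unavailable documents contain.

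**What to change.** At visits 2 and 3, and in the reminder call already made before each appointment, ask every participant the same open question about any change in health since the last contact. Record every event whatever its perceived cause, with onset, severity, outcome and whether product was stopped. State in Data Analysis/Data Monitoring that the number of participants with events will be tabulated by arm with exact confidence intervals. Leave the existing advice to participants unchanged. If the visit session record or consent form already contains such a question, refer to it in the protocol and add only the tabulation.

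The cost is one question at each contact and one form line per visit, with no extra staff. The downside is that more minor, unrelated events will be recorded.

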Potential participants will be screened by telephone and have the study explained to them in detail. If they qualify and choose to participate they will come in for the first of three visits. Informed consent will be obtained and demographic information collected. Information requested on the demographic form includes ethnicity, income, education, marital status, smoking and alcohol use, and exercise habits. Next they will have blood pressure checked and if not within parameters they will be dropped from the study and informed that they need to follow up the abnormal result with their health care provider. They will receive \$20.00 partial compensation for their time. Next a finger stick blood glucose check will be done to rule out diabetes. If their result falls out of the specified parameter range they will be dropped from the study and informed that they need to follow up the abnormal result with their health care provider. They will receive \$20.00 partial compensation for their time. Those that pass these screening tests will have 15 to 25 cc's of peripheral blood (serum) collected by the study coordinator via venipuncture while at rest. They will then stretch for 2 minutes (60 seconds marching in place followed by 10 toe touches) followed by accelerating treadmill walking exercise. The exercise intervention will consist of a 15 minute period of walking on a treadmill. The treadmill will not be inclined during the intervention. The participants target heart rate will be determined by deducting their age from 220. They will start walking on the treadmill at a speed of 1.7 mph and the speed will be titrated as indicated to keep their heart rate at 50 to 90% of target. Heart rate will be monitored via the pulse oximetry feature of the Welch Allyn vital signs monitor. Blood pressure will be measured every 3 minutes during the exercise intervention and until they have returned to baseline (within 10 points) following cessation of the exercise protocol. The test will be stopped for any participant complaint of chest pain, excess fatigue, difficulty breathing, a blood pressure reading of more than 180/94, or a participant request. If symptoms increase or do not completely resolve with 15 minutes of rest the study coordinator will call 911 (through campus police) to activate the EMS response. If symptoms resolve completely within 15 minutes participants will be withdrawn from the study and advised to follow up with their health care provider. Any participant unable to complete the exercise intervention for any reason will be withdrawn from the study.

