- Have severe co-morbid disease including cardiac, pulmonary, renal, hepatic, carotid, peripheral vascular disease, stroke, neurological, clotting disorders or active cancer (*defined as any condition that would cause severe limitations or inability to carry out usual activities of daily living*);
 - Have used any prescription or non-prescription products for antioxidant regimen or stem cell supplement in the 2 weeks prior to beginning this study (Alpha Tocepheral, Vitamin E, Ascorbic Acid, CoQ10)
 - Are diabetic (as defined by diagnosis, use insulin, or a fasting blood glucose value of greater than 120 mg/dl);
 - Have uncontrolled hypertension as evidenced by one of the following;
 - Systolic blood pressure (SBP) > 180 mm Hg or diastolic blood pressure (DBP) > 100 mm Hg, upon two of three repeated measures, if not on medications for hypertension.
 - Systolic blood pressure (SBP) > 150 mm Hg or diastolic blood pressure (DBP) > 90 mm Hg, upon two of three repeated measures, if on medications for hypertension;
 - Have had a recent cardiovascular event (past 36 months), or a family history of sudden death or heart attacks before the age of 55;
 - Have a Body Mass Index (BMI) of less than 20 or greater than 35 m/kg²;
 - Have participated in a clinical trial in the past 4 weeks;
 - Take methadone, insulin, anticoagulants (blood thinners), MAO's or similar medications;
 - The anticipated need for surgery of any type during the entire study;
 - Subjects who plan to donate blood or blood products during the study or for thirty (30) days following the study;
 - Subjects with evidence of active peptic ulcer disease (vomiting of blood, dark blood in stools or stools that are black or tarry, nausea or vomiting, unexplained weight loss, unexplained appetite changes, abdominal pain) or who have a reliable history of gastrointestinal bleeding within the past five (5) years;
 - Subjects with recurrent or a history of intestinal disorders that may interfere with the absorption of the product (Malabsorption Syndrome, Crohns, IBS, Ulcerative Cloitis, gastric bypass).
 - Have any disease or condition that in the investigator's opinion compromises the integrity of the clinical trial or the safety of the subject;

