At your 1st visit you will read and sign a consent form and give us some demographic information. We will check your blood pressure and glucose and BMI to make sure they are within normal limits. If they are not we will not be able to have you continue in the study. We will compensate you \$20.00 for your time if that happens.

If these tests are normal we will collect your blood, have you walk on the treadmill and then collect your blood again. You will receive your supplement of placebo to

NCT01847027

take for the next 4 weeks. If you are able to complete this visit you will receive \$40.00 to compensate you for time and travel.

If we are unable to collect your blood at any visit we will have to drop you from the study and you will receive partial compensation of \$20.00 for your time.

At your 2nd visit we will check your blood pressure & if normal we will collect your blood specimen followed by having you walk on the treadmill again. 5 to 15 minutes after that we will again collect the blood sample. You will receive \$60.00 compensation for completing this visit.

At your 3rd & last visit we will check your blood pressure & if normal we will collect your blood specimen followed by having you walk on the treadmill again. 5 to 15 minutes after that we will again collect the blood sample. You will receive \$80.00 compensation for completing this visit.

Do you have any questions or concerns? discuss as appropriate

If you are still interested I need to ask you some questions to determine if you qualify to participate in this study. If yes;

Age: _____
(Men/women age 50 to 70)

Difficult blood draw: _____
(exclude if self reported history of difficult veins/difficulty obtaining blood sample)

How much exercise: _____
(exclude if more than 2 sessions per week of strenuous exercise in the last month)

Food allergies _____
(exclude if any)

Diabetic: _____
(exclude if diabetic by diagnosis and/or use insulin or oral diabetic meds)

Hypertension: _____
(exclude if not controlled, under 180/100 not on meds, 150/90 on meds)

Unintentional weight loss/gain: _____
(exclude if lost or gained 10 or more pounds in the last 3 mos)

IRB APPROVED

JAN 04 2013

Current acute cold/flu other: _____
(exclude if yes)

NCT01847027

Hospitalization in last month: _____
(exclude if yes)

Chronic illness:

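### Unmedicated participants can enter with resting diastolic pressure up to 100 mmHg, yet the treadmill stops above 180/94, so a resting diastolic of 95 to 100 meets the entry limit while already above the stop reading

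*Combined protocol and SAP*

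**What the plan says.** **Entry.** In section F, Exclusion Criteria, people not on antihypertensive medication are excluded for "Systolic blood pressure (SBP) > 180 mm Hg or diastolic blood pressure (DBP) > 100 mm Hg, upon two of three repeated measures". For people on medication the rule is "Systolic blood pressure (SBP) > 150 mm Hg or diastolic blood pressure (DBP) > 90 mm Hg, upon two of three repeated measures". The telephone screening script carries the same pairs of limits: "exclude if not controlled, under 180/100 not on meds, 150/90 on meds".

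**Visit checks.** For visit 1, section E says "Next they will have blood pressure checked and if not within parameters they will be dropped from the study". For visit 2 it says "If the blood pressure is outside of the specified range they will be dropped from the study and no blood collection or study intervention" will follow, and visit 3 is run the same way. Neither place gives a number for these checks. The script describes them in terms of normal pressure, also without a number.

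**Stopping.** The visit 1 description and the Exercise stimulus section both have: "The test will be stopped for any participant complaint of chest pain, excess fatigue, difficulty breathing, a blood pressure reading of more than 180/94". The Potential Risks part of section G uses the same 180/94. On monitoring: "Blood pressure will be measured every 3 minutes during the exercise intervention". On the consequence: "Any participant unable to complete the exercise intervention for any reason will be withdrawn from the study".

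**The concern.** The limit that lets an unmedicated person onto the treadmill is looser, for diastolic pressure, than the limit that takes the person off it. The plan therefore allows exercise to begin at a pressure that it treats as a reason to stop.

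Two things are at stake.

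- **Safety rule.** The coordinator has no instruction for a participant who is eligible and already above the stop reading. Potential Risks also calls emergency services if raised pressure has not resolved after 15 minutes of rest. It does not say what resolved means for someone whose usual diastolic is 95 to 100.
- **Data.** At visit 1 such a person consents, gives a resting sample and is lost before product is dispensed. At visit 2 or 3 the loss comes after randomisation and 2 or 4 weeks of product. That visit's post-exercise sample and all later samples are then missing. Stem cell levels with the exercise stimulus are the study's aim, there are at most 30 participants per arm, and Data Analysis/Data Monitoring gives no rule for missing visits in its repeated measures ANOVA.

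**Working it through.** The plan has no figure of its own to reproduce here. The check compares its limits.

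**1. Headroom = stop reading − highest admitted resting reading.** Entry limits are from the Exclusion Criteria, the stop reading from Exercise stimulus.

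| Group | Component | Admitted up to | Stop above | Headroom (mmHg) |
|---|---|---|---|---|
| Unmedicated | Systolic | 180 | 180 | 180 − 180 = 0 |
| Unmedicated | Diastolic | 100 | 94 | 94 − 100 = −6 |
| Medicated | Systolic | 150 | 180 | 180 − 150 = 30 |
| Medicated | Diastolic | 90 | 94 | 94 − 90 = 4 |

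Only the unmedicated diastolic limit conflicts. The six whole-number values 95 to 100 are eligible and above the stop reading.

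**2. Strictness.** Entry fails on two of three readings; the stop acts on one. Resting diastolics of 98, 104 and 99 pass entry, because only one exceeds 100, yet all three exceed 94.

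**3. What must happen for the test to continue.** With resting diastolic D from 95 to 100, the 3-minute reading must be at least D − 94 lower, that is 1 to 6 mmHg. Otherwise the test stops and the withdrawal rule applies.

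**4. Illustration of size (assumptions, not trial data).** Suppose resting diastolic among unmedicated volunteers is normal with SD 10 and mean m, recorded in whole mmHg. The share of those admitted who are at 95 to 100 is

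[Φ((100.5 − m)/10) − Φ((94.5 − m)/10)] / Φ((100.5 − m)/10).

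For m = 80 this is (0.9798 − 0.9265)/0.9798 = 0.054. For m = 76 it is 0.025, and for m = 84 it is 0.102.

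For visits 2 and 3, I simulated participants who were at 94 or below at visit 1, with a between-visit correlation of 0.6 to 0.8 and one reading per visit. I counted those above the stop reading at either later visit who were not dropped for exceeding 100. The same assumed fall on walking is applied at every visit. Counts are per 60 participants, all taken as unmedicated.

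| Fall in diastolic on walking | Visit 1 (m = 76, 80, 84) | Visits 2–3 (range over m and correlation) |
|---|---|---|
| 0 mmHg | 1.5, 3.3, 6.1 | 1.6 to 7.4 |
| 3 mmHg | 0.5, 1.2, 2.5 | 0.5 to 2.9 |
| 6 mmHg | 0, 0, 0 | 0 |

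If half the participants are medicated, each count halves. The visits 2–3 column already assumes 94 or below at visit 1, so an entry limit of 94 does not reduce it.

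**The case against.** **The visit check may be tighter than the entry criteria.** The script speaks of normal pressure at each visit, and the range used at visits 2 and 3 is not defined. A diastolic of 95 to 100 might be turned away on the day. The investigator-opinion exclusion could do the same. This stands in part: one cannot say that such a person will certainly pass and start walking. But neither provision sets a number, and the only numbers in the script are 180/100 and 150/90.

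**The stop reading could mean both components.** If both must be exceeded, only people near 180 systolic are affected. The text does not settle this. The either-component reading is more natural: the exclusion criteria join systolic and diastolic with an or, and a both-components rule would let exercise continue at, say, 175/110.

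**The stop rule still works.** The exercise is flat walking starting at 1.7 mph, read every 3 minutes, with a registered nurse who may end it on her own judgement. This stands. A reader might infer that participants are left exercising without protection; the documents do not support that. The mismatch errs toward stopping.

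**The systolic limit.** A reader might infer that the whole unmedicated limit should come down, for example to 160/90. There is no systolic overlap to justify 160. A diastolic limit of 90 would also turn away people at 91 to 94 who are below the stop reading.

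**Conclusion.** The inconsistency holds, for diastolic pressure in unmedicated participants. Its size is a 6 mmHg overlap, which follows from the stated limits without any assumed distribution. It rests on two readings of the text: that either component above its value triggers the stop, and that the visit checks use the Exclusion Criteria limits.

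A reader might infer from the table that a particular number of participants will be lost. The documents do not support this. They give no blood pressure distribution, medicated share, between-visit correlation or response to walking. The illustrative counts run from 0 to about 7 of 60 at visits 2–3, depending on those choices. The point should be acted on because the plan contradicts its own safety limit, because withdrawals after randomisation from this cause are avoidable, and because the correction is short.

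**What to change.** 1. In section E (visits 1 to 3) and Exercise stimulus, state that the treadmill is not started at any visit when resting pressure is above 180 systolic or above 94 diastolic. State that the same either-component rule governs stopping.
2. In the Exclusion Criteria and the screening script, lower the unmedicated diastolic limit from 100 to 94. Leave the systolic limit and the medicated limits unchanged.
3. At visits 2 and 3, when the resting reading is too high, re-measure after rest or rebook within a few days before withdrawing a randomised participant.

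Item 2 removes the overlap at entry. Items 1 and 3 are still needed, because entry is judged on two of three readings and pressure varies between visits.

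The cost is one IRB amendment, slight flexibility in the 2-week visit interval with a few extra capsules for rebooked visits, and volunteers at 95 to 100 turned away at entry. Under the assumptions above that is 1.5 to 6.1 per 60 admitted if all are unmedicated. The plan would expect to stop these people anyway, apart from any whose diastolic falls far enough on walking.
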